7.5 Contraceptive Use

Female patients of childbearing potential, or male patients who have partners with childbearing potential, have to take appropriate measures to prevent pregnancy for at least 28 days prior to the first administration of the study drug, during the study, and for at least 3 weeks after the last dose of the study drug. A woman is considered of childbearing potential (WOCBP), i.e. fertile, following menarche and until becoming post-menopausal unless permanently sterile. Permanent sterilization methods include hysterectomy, bilateral salpingectomy and bilateral oophorectomy.

A postmenopausal state is defined as no menses for 12 months without an alternative medical cause. A high follicle stimulating hormone (FSH) level in the postmenopausal range may be used to confirm a post-menopausal state in women not using hormonal contraception or hormonal replacement therapy. However, in the absence of 12 months of amenorrhea, a single FSH measurement is insufficient.

Additionally, if the participant is using systemic contraceptives, she must use an additional non-hormonal form of acceptable method of contraception during the study and for at least 30 days after the last dose of the study drug.

7.6 Washout

There will be a 7-day washout period before initial treatment with study drug, a second 7-day washout after the crossover and before treatment with the second study drug, and a third 7-day washout period at the end of the study on Day 63.

7.7 Eligibility Review

Eligibility criteria are reviewed at the visits prior to randomization. If laboratory values are abnormal, the test may be repeated within an interval (to be determined) that allows results to be reviewed prior to randomization.

Screen Failure: A screen failure is defined as a patient who consented but who has not been randomized.

7.8 Clinical Assessments

Vital signs will be assessed as described in Table 6-1.

Resting blood pressure, heart rate, respiratory rate, and body temperature will be measured at Screening, and Days 1, 14, 28, 36, 49, and 63.

7.9 Physical Examination

Physical examinations will be performed as described in Table 6-1. The examination will be brief or complete as follows:

- A brief physical examination consisting of an evaluation of the head, neck, eyes, ears, nose, throat, chest, heart, lungs, abdomen, skin, extremities, and the neurological and musculoskeletal systems will be performed on Days 1, 14, 36, and 49.

- A complete physical examination consisting of an evaluation of the general body, skin, head, neck, eyes, ears, nose, throat, chest, heart, lungs, abdomen, extremities, and the neurological and musculoskeletal systems will be performed at Screening, Day 28, and on Day 63.

Any clinically significant finding observed at the baseline visit before dosing on Day 1 will be considered medical history. Any new or worsened clinically significant finding observed at a post-randomization visit will be considered an adverse event.

7.10 Ferritin Monitoring

Ferritin (mcg/L) will be assessed in serum or plasma (at Screening, Eligibility and on Days 1, 28, 36 and 63) with enzyme-linked immunosorbent assays (ELISA) by routine laboratory methods.

7.11 Laboratory Assessments and Procedures

7.11.1 Laboratory Assessments

Laboratory assessments will be performed at scheduled visit as described in Table 6-1.

Safety laboratory tests selected include comprehensive metabolic panel (sodium, potassium, chloride, carbon dioxide, glucose, blood urea nitrogen, creatinine, calcium, total protein, albumin, AST, ALT, alkaline phosphatase, and total bilirubin); complete blood count (white blood cell count, hemoglobin, hematocrit, platelet count, differential); PT and PTT; standard urinalysis panel (pH, protein, glucose, ketone, color, specific gravity, occult blood, leukocyte esterase, nitrite, bilirubin, and urobilinogen) and serum CRP.

Urine will be collected for the assessment of protein and creatinine on Days 1, 14, 28, 36, 49 and 63 of both treatments.

Urine pregnancy tests will be conducted on all women of childbearing potential at Screening.

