4.1 Inclusion Criteria

1. Written informed consent obtained prior to any study-related procedure being performed;
2. Patients at least 18 years of age or older at the time of consent;
3. Patient with TDT or NTDT syndromes and iron overload currently receiving iron chelation therapy with Jadenu or Exjade and demonstrating inadequate response assessed with serum ferritin and LIC;
4. Stable dosing with Jadenu or Exjade for >3 months prior to screening and receiving the maximal dose (Jadenu: 28 mg/kg or Exjade: 40 mg/kg);
5. Serum ferritin levels that are persistently >800 mcg/L determined by 2 separate assessments during screening over the previous 2-4 weeks prior to study treatment and not showing a decreasing trend over these weeks;
6. An LIC of >5 mg Fe/g dw measured by MRI in the 52 weeks prior to study entry;
7. Compliant with chelation therapy in the 3 months prior to enrollment as assessed by the Investigator:
 - a. Satisfaction with Iron Chelation Therapy (SICT) Quality of Life (QoL) composite score $\geq 60\%$, or determined by investigator that at least 75% of medication prescribed on a regular basis was taken (Investigator enquiry into patient prescription refill records, preferably 3 months if available); and
 - b. Willing to comply with chelation therapy for the duration of the study;
8. Agree not to use other anti-chelating agents concurrently;
9. Eastern Cooperative Oncology Group Performance Status (ECOG PS) of 0-1;
10. Women of childbearing potential (WOCBP) must use an adequate method of birth control (double barrier, e.g. hormonal control and barrier contraception) at least 28

days prior to the first administration of the study drug, during the study and for at least 30 days after the last dose of the study drug. (Section 7.5 for details);

11. Male patients whose partners are WOCBP must use an adequate method of birth control (double barrier control) at least 28 days prior to the first administration of the study drug, during the study and for at least 30 days after the last dose of the study drug; and
12. Patient is willing and able to comply with all protocol required visits and assessments.

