4.2 Exclusion Criteria

1. Patients with life expectancy less than 6 months;
2. Females of childbearing potential not on an adequate method of birth control, or who are pregnant or lactating;
3. History of non-compliance with chelation therapy (determined by the investigator, persistently taking less than 75% of prescribed dose in the 3 months prior to enrollment, or as determined by the Investigator based on medical history, SICT QoL overall score <60% or score in any SICT domain <50%);
4. Screening blood counts of the following:
 - a. Absolute neutrophil count < 1500/ μ L
 - b. Platelets < 100,000/ μ L
 - c. Hemoglobin < 8 g/dL; transfusion support is permitted;
5. Screening chemistry values of the following:
 - a. Alanine aminotransferase (ALT) and aspartate transaminase (AST) > 2.5 \times upper limit of the normal reference range (ULN)
 - b. Total bilirubin > 2 \times ULN
 - c. Creatinine > 1.5 \times ULN
 - d. Urine protein/creatinine ratio (UPCR) >0.5 mg/mg
 - e. Albumin < 2.8 g/dL;
6. History of congestive heart failure New York Heart Association (NYHA) class III or IV or uncontrolled hypertension at screening;

7. History of other malignancy within the previous 3 years, except basal cell or squamous cell carcinoma, or non-muscle invasive bladder cancer;
8. In the opinion of the Investigator, evidence of major inflammatory disease that would affect ferritin levels within 14 days prior to the start of study medication;
9. Major surgery within 30 days prior to the start of study medication;
10. Serious persistent infection within 14 days prior to the start of study medication;
11. Serious concurrent medical condition including central nervous system (CNS) disorders;
12. Requires concomitant treatment with systemic corticosteroids, or any other immunosuppressive agents, or has used such treatment in the past 10 days before study entry (use of prednisone or equivalent <10 mg/day orally or use of inhaled corticosteroids or topical steroids is permitted).
13. Previous history of difficulty swallowing oral medications;
14. Any condition that, in the opinion of the Investigator, would impair the patient's ability to comply with study procedures or study medication; or
15. Concomitant treatment with medications described in [Section 7.4](#) "Prohibited Medications".

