6.1 Screening (Visit 1; Days -28 to -15)

Procedures as identified in Table 6-1.

- Written Informed Consent
- Medical and surgical history
- Prior medications
- Body weight and height
- Eligibility review
- Vital signs (blood pressure, heart rate, respiratory rate and body temperature)
- Physical examination (full)
- Chemistry, hematology (CBC) and urinalysis
- Serum C-reactive protein (CRP)
- Urine Pregnancy Test (women of childbearing potential only)
- Urine for protein and creatinine
- ECOG PS (see [Appendix C](#))
- Concomitant medications
- Dispense gastrointestinal AESI diary
- Dispense Bristol Stool Chart and diary
- Ferritin monitoring
- Trough PK sampling

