6.6 Early Termination Procedures

The term "Early Termination" refers to a patient's non-completion of a study whether by his or her own choice or the Investigator's decision or due to discontinuation of the study by DisperSol.

In the absence of a medical contraindication or significant protocol violation, every effort will be made by the Investigator to keep the patient in the study. Should the patient decide to

withdraw, an attempt will be made to conduct an early termination visit, which will include all procedures normally done at Visit 10 (Day 63) and, the patient should be requested to undergo a 7-day washout and have a phone call to confirm as in the Follow-up (Day 70) procedures.

The primary reason for a patient withdrawing prematurely should be selected from the following categories:

Adverse Event or Serious Adverse Event - events that are associated with discontinuation.

Noncompliance with protocol - The patient failed to adhere to the protocol requirements. The deviation necessitated premature termination from the study.

Pregnancy - The patient became pregnant after enrolling the study. Pregnant patients are withdrawn from the study as soon as the Principal Investigator is aware of the condition.

Laboratory Abnormality - Laboratory abnormality that does not meet the definition of an AE.

Withdrawal of Consent - The patient desires to withdraw from further participation in the study in the absence of an adverse event or a medical need to withdraw.

Lost to Follow-up - The patient did not return for follow-up visit(s) following dispensing of test drug.

Other - causes of premature termination from the study other than the above, such as theft or loss of investigational product, termination of study by DisperSol, etc.

The Investigator should notify Accelovance, Inc. promptly when a patient is withdrawn, or if the study is stopped at his/her site by the IRB or if the Investigator elects to stop the study.

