9.2 Procedures

An untoward event that occurs after screening and before the first dose of investigational product will be recorded as an update to the medical history.

Some events may make the patient ineligible for randomization. Unanticipated events should be reported to the IRB, according to its requirements.

Patients will be questioned at every visit after the first dose until Visit 11 or ET regarding the occurrence and nature of any AEs. All AEs will be reported, whether or not they are deemed to be related to investigational product.

A description of the event or diagnosis including dates, severity, relationship to the investigational product, action taken with the study drug and outcome, and whether or not the event was also serious, must be reported on the AE CRF for each adverse event recorded in the patient's chart.

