17 PATIENT COUNSELING INFORMATION

- Advise patients to take JADENU once daily, on an empty stomach or with a light meal, (contains less than 7% fat content and approximately 250 calories) preferably at the same time every day [see *Dosage and Administration (2.3)*]. Examples of light meals include 1 whole wheat English muffin, 1 packet jelly (0.5 ounces), and skim milk (8 fluid ounces) or a turkey sandwich (2 oz. turkey on whole wheat bread w/ lettuce, tomato, and 1 packet mustard).
- Advise patients to take the tablet with water or other liquids [see *Dosage and Administration (2.3)*].
- Advise patients to store JADENU in a dry, room-temperature environment [see *How Supplied/Storage and Handling (16)*].
- Caution patients not to take aluminum-containing antacids and JADENU simultaneously [see *Drug Interactions (7.1)*].
- Because auditory and ocular disturbances have been reported with deferasirox, conduct auditory testing and ophthalmic testing before starting JADENU treatment and thereafter at regular intervals [see *Warnings and Precautions (5.8)*].
- Caution patients experiencing dizziness to avoid driving or operating machinery [see *Adverse Reactions (6.1)*].
- Caution patients about the potential for the development of GI ulcers or bleeding when taking JADENU in combination with drugs that have ulcerogenic or hemorrhagic potential, such as NSAIDs, corticosteroids, oral bisphosphonates, or anticoagulants [see *Warnings and Precautions (5.3)*].
- Caution patients about potential loss of effectiveness of drugs metabolized by CYP3A4 (e.g., cyclosporine, simvastatin, hormonal contraceptive agents) when JADENU is administered with these drugs [see *Drug Interactions (7.2)*].
- Caution patients about potential loss of effectiveness of JADENU when administered with drugs that are potent UGT inducers (e.g., rifampicin, phenytoin, phenobarbital, ritonavir). Based on serum ferritin levels and clinical response, consider increases in the dose of JADENU when concomitantly used with potent UGT inducers [see *Drug Interactions (7.5)*].

- Caution patients about potential loss of effectiveness of JADENU when administered with drugs that are bile acid sequestrants (e.g., cholestyramine, colesevelam, colestipol). Based on serum ferritin levels and clinical response, consider increases in the dose of JADENU when concomitantly used with bile acid sequestrants [see *Drug Interactions (7.6)*].

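### The only scheduled pregnancy test is 15 to 28 days old at randomisation and first dose, and 50 to 63 days old when the second product starts on Day 36

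*Protocol*

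**What the plan says.** Section 7.11.1 of the protocol fixes the timing: "Urine pregnancy tests will be conducted on all women of childbearing potential at Screening". Section 6.1 lists the test at Visit 1 (Days -28 to -15), and Table 6-1 and its copy in the synopsis carry a single mark for it, in the Visit 1 column. The procedure lists for Visits 2 to 10 (Sections 6.2 to 6.4.4) contain none, and the Day 70 contact is a telephone call.

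Exclusion criterion 2 in Section 4.2 bars "Females of childbearing potential not on an adequate method of birth control, or who are pregnant or lactating". Section 7.7 says "Eligibility criteria are reviewed at the visits prior to randomization", and Table 6-1 places those reviews at Visits 1, 2 and 3. Pregnancy is also withdrawal criterion 7 in Section 4.3, and Section 6.6 adds: "Pregnant patients are withdrawn from the study as soon as the Principal Investigator is aware of the condition".

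On contraception, inclusion criterion 10 says that women of childbearing potential "must use an adequate method of birth control (double barrier, e.g. hormonal control and barrier contraception) at least 28" days before the first dose. Sections 3.2 and 7.5 require a woman on systemic contraceptives to add a non-hormonal method.

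**The concern.** The passages agree with one another; what is badly fixed is the timing. The Day 1 eligibility review can confirm contraception and lactation by asking the patient, but for pregnancy it has only the Visit 1 result. Section 7.7 provides for repeating a laboratory test when the value is abnormal, so a negative Visit 1 result triggers no repeat. After Day 1, the withdrawal rule depends on the investigator becoming aware, and no scheduled test produces that awareness. It would have to come from the patient, from clinical suspicion at a physical examination, or from adverse-event enquiry, for which Section 9.2 says: "Patients will be questioned at every visit after the first dose until Visit 11 or ET regarding the occurrence and nature of any AEs".

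What is at stake is exposure of an unrecognised pregnancy. Participants already take maximal-dose deferasirox, so the trial adds no new drug substance. It does add DST-0509, which is dosed mg for mg with Jadenu (Section 5.4) although Section 1.2 reports higher bioavailability in healthy volunteers. The animal data in Section 8.1 of the Jadenu label (Appendix B) are mixed. Dosing during organogenesis gave maternal toxicity without fetal harm. Dosing from organogenesis through lactation reduced offspring viability at 1.0 times the maximum recommended human dose and produced renal anomalies in male offspring at 0.3 times that dose.

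**Working it through.** The protocol states no age for the test result, so there is no figure of its own to reproduce. The check is calendar arithmetic.

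**Inputs**
- Pregnancy test: Visit 1, Day -28 to Day -15 (Section 6.1, Table 6-1).
- Randomisation and first dose: Visit 3, Day 1 (Sections 5.4 and 7.12).
- Start of the second product: Visit 7, Day 36 ± 1 (Section 6.4.1).
- Last dose: Visit 10, Day 63 ± 1 (Sections 5.4 and 6.4.4).
- No Day 0: Table 6-1 runs the 7-day washout over Days -7 to -1, directly followed by Day 1.

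**Age of the result**

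Without a Day 0, a test on Day -d is d days old on Day 1, and d + (D - 1) days old on Day D.

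| Time point | Latest test (Day -15) | Earliest test (Day -28) | Range with ±1 day window |
|---|---|---|---|
| Day 1 (first dose) | 15 | 28 | none stated |
| Day 36 (second product) | 15 + 35 = 50 | 28 + 35 = 63 | 49 to 64 |
| Day 63 (last dose) | 15 + 62 = 77 | 28 + 62 = 90 | 76 to 91 |

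Counting a Day 0 would add one day to each figure and change nothing of substance.

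**Opportunities to test**
- Clinic visits after Visit 1: Visits 2 to 10, which is 9. Pregnancy tests among them: 0.
- Visits at which urine is collected anyway: Visits 3, 5, 6, 7, 9 and 10 (Days 1, 14, 28, 36, 49 and 63), which is 6.

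**How far contraception closes the gap**
- The requirement begins 28 days before first dose, that is on Day -28, which is also the earliest permitted Visit 1 day. A woman tested on Day -28 may therefore have had no required contraception before her only test, and a very recent conception might not yet show.
- A conception after Visit 1 requires contraceptive failure or non-adherence. The protocol's own example pairs a hormonal with a barrier method, and the patient counselling sections of both appended labels warn of "potential loss of effectiveness of drugs metabolized by CYP3A4 (e.g., cyclosporine, simvastatin, hormonal contraceptive agents". In that case the non-hormonal method carries more of the protection.

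**Effect of testing at Visits 3 and 7**
- The result would be 0 days old at each product start.
- On nominal days it would be 28 - 1 = 27 days old at the end of Period 1 and 63 - 36 = 27 days old at the end of Period 2.
- A repeat at Visit 2 alone (Days -14 to -8) would still be 8 to 14 days old at first dose.

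**The case against.** The strongest reply is that nothing in the protocol is misstated and that it sets no testing frequency which this schedule misses. The appended labels prescribe several checks before and during treatment, but they schedule no pregnancy test and do not list pregnancy among the contraindications. That is true. The case does not rest on the labels: the protocol makes pregnancy an exclusion reviewed again on Day 1, and gives that review no current result.

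A second reply is that contraception is strict. It must be in place by Day -28, and any woman on a systemic method must add a non-hormonal one, which the hormonal interaction does not affect. This stands as mitigation and narrows the gap to a conception shortly before an early Visit 1, or to failure of both methods later. It does not close it.

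A third reply is that one of the two product starts is the patient's own Jadenu or Exjade at her usual dose (Day 36 in Sequence A, Day 1 in Sequence B), so a single test before DST-0509 would do. This has some force. Yet the exclusion applies before the sequence is known, so everyone needs the Day 1 test, and Sequence B then starts DST-0509 on Day 36. With 18 patients per sequence the narrow version needs 36 + 18 = 54 tests at most, against 72. Each start also follows a 7-day washout. With the half-life of 8 to 16 hours in Section 1.1, 168 hours is 168/16 = 10.5 to 168/8 = 21 half-lives, so the trial restarts exposure from near zero on both days and in both sequences.

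Finally, higher exposure on DST-0509 is inferred from single-dose studies in healthy volunteers; multiple-dose exposure in patients is not given. That uncertainty is real and limits what can be said about the animal margins. Withdrawal on awareness (Section 6.6) and 24-hour reporting (Section 9.9) act only once a pregnancy is known.

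**Conclusion.** The concern holds. A site following the protocol exactly will randomise and first dose women of childbearing potential on a pregnancy result 15 to 28 days old, and start the second product on one 50 to 63 days old (49 to 64 with the window). These ages assume no Day 0, as the washout days in Table 6-1 show, and Visit 1 held within its stated window.

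This is a patient-safety safeguard that should be tightened. It is not an internal contradiction and it alters no sample-size or analysis figure. The protocol gives no basis for the probability of pregnancy, and none is assumed.

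**What to change.** In Table 6-1 and its synopsis copy, and in Sections 6.3.1, 6.4.1 and 7.11.1, add a urine pregnancy test for women of childbearing potential at two visits:

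- **Visit 3 (Day 1):** read before randomisation. A positive result is a screen failure under exclusion criterion 2.
- **Visit 7 (Day 36):** read before Period 2 dosing. A positive result leads to withdrawal under Section 4.3, criterion 7.

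Use the urine already collected at both visits. The cost is two inexpensive tests per woman of childbearing potential, at most 2 × 36 = 72 if every patient were such a woman. No visit, sample or invasive procedure is added. The only burden is waiting for the result before randomisation and before the Period 2 dose.

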7.11.2 Pharmacokinetics

Trough samples will be collected at Visit 1 and 2. Blood samples for PK analysis will be collected predose (-0.5 hour) and at 1, 2, 4, and 8 hours postdose on Days 1, 7, 28, 36, 42 and 63. The allowed sampling “window” is ± 15 min for the 1 and 2 hour time points, and ± 30 min for the 4 hour time point. For the 8 hour time point, the allowable window is ± 1 hour.

7.11.3 Collection, Shipment, and Retention of Laboratory Samples

All safety laboratory analyses will be performed by either a central or local laboratory. If a central laboratory is utilized, central laboratory will provide all collection materials and instructions for sample collection, packaging, and shipment. Samples for chemistry, hematology (CBC) and urinalysis will be collected at Screening and on Days 1, 14, 28, 36, 49 and 63. Samples for serum CRP will be collected at Screening and on Days 1, 28, 36, and 63.

